#### Software

Pharmacokinetic parameters will be derived using noncompartmental methods with the validated computer program Phoenix® WinNonlin® 6.4 or higher (PPD

Description of the program Phoenix® WinNonlin® 6.4 or higher (PPD)

Description of the program Phoenix® WinNonlin® 6.4 or higher, or SAS® Windows Version 9.4 or higher (PPD)

Description of the program Phoenix® WinNonlin® 6.4 or higher, or SAS® Windows Version 9.4 or higher (PPD)

Description of the program Phoenix® WinNonlin® 6.4 or higher, or SAS® Windows Version 9.4 or higher (PPD)

Description of the program Phoenix® WinNonlin® 6.4 or higher (PPD)

Description of the program Phoenix® WinNonlin® 6.4 or higher (PPD)

Description of the program Phoenix® WinNonlin® 6.4 or higher (PPD)

Description of the program Phoenix® WinNonlin® 6.4 or higher (PPD)

Description of the program Phoenix® WinNonlin® 6.4 or higher (PPD)

Description of the program Phoenix® WinNonlin® 6.4 or higher (PPD)

Description of the program Phoenix® WinNonlin® 6.4 or higher (PPD)

Description of the program Phoenix® WinNonlin® 6.4 or higher (PPD)

Description of the program Phoenix® WinNonlin® 6.4 or higher (PPD)

Description of the program Phoenix® WinNonlin® 6.4 or higher (PPD)

Description of the program Phoenix® WinNonlin® 6.4 or higher (PPD)

Description of the program Phoenix® WinNonlin® 6.4 or higher (PPD)

Description of the program Phoenix® WinNonlin® 6.4 or higher (PPD)

All other statistical analyses will be performed using SAS® version 9.4 or higher.

#### Presentation of continuous and qualitative variables:

Continuous variables will be summarized using the following descriptive statistics unless otherwise specified, i.e.,

- number of subjects (N), number of subjects with non-missing values
- mean, SD
- median, 25th Percentile 75th Percentile (Q1-Q3)
- minimum and maximum

Qualitative variables will be summarized by counts and percentages.

Unless otherwise stated the calculation of proportions will be based on the number of subjects of the analysis set of interest. Therefore, counts of missing observations will be included in the denominator and presented as a separate category.

In case the analysis refers only to certain visits, percentages will be based on the number of subjects still present in the trial at that visit, unless otherwise specified.

#### **Definition of baseline:**

Baseline for assessments is defined as the last non-missing measurement taken prior to or on the day of the first trial drug administration.

For vital signs and electrocardiogram (ECG), an assessment performed on dosing date with time point marked as "predose" will be considered as baseline. If there is no time point, the last non-missing assessment prior to dosing will be taken as baseline.

In the case where the last non-missing measurement and the dosing date/time coincide, that measurement will be considered baseline, but AEs and medications commencing on the reference start date will be considered post baseline. Such as AE happened on dosing date (even AE before dosing, and there is no time to make judgement) it will be treated as a TEAE.

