7.3.1.2 Methods of Recording and Assessing Adverse Events

At each trial visit, the subject will be queried on changes in his condition. During the reporting period of the trial any unfavorable changes in the subject's condition will be recorded as AEs, whether reported by the subject or observed by the Investigator.

All AEs must be documented in the appropriate section of the eCRF. Complete, accurate and consistent data on all AEs experienced for the duration of the reporting period (defined below) will be reported on an ongoing basis. Among these AEs, all serious AEs must be additionally documented and reported using an SAE Report Form (Clinical Trial) as described in Section 7.3.1.4.

The following aspects must be recorded for each AE in the eCRF:

- 1) Description of the AE in medical terms, not as reported by the subject
- 2) Date/time of onset (only in relation to administration of IMP: before, during, or after)
- 3) Severity grade (Section 7.3.1.1), assessed by the Investigator according to the Qualitative Toxicity Scale
- 4) Causal relationship to the IMP applied per protocol, assessed by the Investigator
- 5) Action taken with regard to trial treatments
- 6) Concomitant medication
- 7) Outcome
- 8) Seriousness (appropriate criteria documented).

Specific guidance can be found in the eCRF Completion and Monitoring Conventions provided by the Sponsor.

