8.2.4.4 Analysis of Safety Endpoints

All data recorded during the trial will be presented in individual data listings performed on the safety population.

All safety variables will be analyzed using descriptive statistics.

For the evaluation of safety parameters, the continuous variables will be summarized descriptively per treatment, period, time point, and overall by N, arithmetic mean, median, standard deviation (SD), standard error of the mean (SEM), and minimum and maximum values. Categorical variables will be presented in frequency tables with the counts of observations and corresponding percentages.

Blood pressures, pulse rate measurements and ECG recordings will be individually listed by treatment, subject number, period, and time point, and the abnormal values flagged according to reference laboratory ranges. All hematology and biochemistry parameters will be listed and summarized using descriptive statistics by treatment, period, and time point on observed values. Urinalysis will be summarized in frequency tables.

After coding of AEs according to the Medical Dictionary for Regulatory Activity classification (current version) and assignment to a system organ class and preferred term, all AEs recorded during the course of the trial will be listed by treatment and subject number.

The AE listings will include the following items:

- System organ class
- Preferred term
- Investigator's description
- Whether the event is treatment-emergent
- Trial treatment at onset of event
- Date and time of onset and resolution
- Duration of the event
- Date and time of last administration before AE
- Intensity
- Causality relationship to investigational product
- Outcome

- Action taken to investigational product
- Other action
- Seriousness

Incidence of treatment-emergent adverse events will be summarized using frequency of events and number of subjects experiencing these events per treatment, preferred term, and system/organ class.

In addition, all treatment-emergent adverse events will be tabulated by intensity and relationship to drug per treatment and cohort. An AE will be considered "treatment-emergent" if it occurred after the first investigational product administration or if it occurred before the first investigational product administration and worsened after.

Results of physical examination will only be listed by treatment, subject, period, time point, and body system.

Handling of discontinued subjects and missing data

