#### Handling of missing data:

Unless otherwise specified, missing data will not be replaced. Handling of missing data for PK parameter calculations are discussed under Section 16.3.3.

In all subject data listings imputed values will be presented. In all listings imputed information will be flagged.

Missing statistics, e.g., when they cannot be calculated, should be presented as "nd". For example, if n=1, the measure of variability (SD) cannot be computed and should be presented as "nd".

For the derivation of new date variables the following rules will apply:

Partial birth dates will be handled this way: day will be imputed as 15 if it is missing, and month imputed as June if missing. If both of day and month are missing, they will be imputed as July 1st. If year is missing then the date will not be imputed.

Any adverse event (AE) with incomplete start and or end dates/times will be handled as described below for the classification as treatment-emergent, assignment to treatment periods and calculation of duration.

• Adverse events with unknown start times but known start dates, will be imputed with a time of 00:00 hours, unless the start date corresponds to any given dosing date, in which

case time of dosing will be used instead. However, if this results in a start time after end time of the AE, then the start time will be imputed to 00:00 hours instead.

- Any adverse event with completely unknown start dates will be imputed with date and time of the first administration of a study drug, unless the end date is known and prior to first administration. In the latter case, the start date will be imputed as the date of screening and a time of 00:00 hours.
- Adverse events with completely unknown end times, will be imputed with an end time of 23:59 hours.
- Adverse events with completely unknown end dates will be imputed with the date of study completion (or in case of withdrawal, date of discontinuation).

Partially known end dates will be treated as follows:

- If only the day is missing, the last day of the month will be imputed or the date of study completion/discontinuation if earlier.
- If day and month are both missing, then the end date of 31 December will be imputed or the date of study completion/discontinuation if earlier.

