Assignment to the different treatment periods will be performed after the imputations have been performed. An AE will be assigned to a specific treatment period if it occurs after the IMP administration scheduled for that period and before the IMP administration in the next period (or study completion for the last period).

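### An untimed adverse event on a dosing day is set to the dosing time and counted as treatment-emergent even if it was recorded as starting before the dose (minor)

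*SAP*

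**What the plan says.** Protocol 7.3.1.2 lists what must be recorded for each adverse event (AE). The onset item reads "Date/time of onset (only in relation to administration of IMP: before, during, or after". Protocol 8.2.4.4 and SAP 17.1 both put "Date and time of onset and resolution" among the items of the AE listings.

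SAP Section 11 has two sets of rules for an AE whose start time is not known.

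- Under the definition of baseline, following a sentence about AEs that begin on the reference start date: "AE happened on dosing date (even AE before dosing, and there is no time to make judgement) it will be treated as a TEAE".
- Under the handling of missing data, an unknown start time becomes 00:00 "unless the start date corresponds to any given dosing date"; for those dates, "case time of dosing will be used instead". There is one exception: "if this results in a start time after end time of the AE, then the start time will be imputed to 00:00 hours instead". An unknown end time becomes 23:59.

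On the order of steps the SAP says "Assignment to the different treatment periods will be performed after the imputations have been performed". The period rule is "An AE will be assigned to a specific treatment period if it occurs after the IMP administration scheduled for that period" and before the dose of the next period.

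SAP 17.1 defines a treatment-emergent AE (TEAE) as one that occurs after the dose of a period, or was present earlier and worsened after it. Every other AE is pre-treatment. SAP 17.1 defaults to TEAE only where the status cannot be established. Protocol 8.2.4.4 also requires onset, or worsening, after the first dose.

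**The concern.** The protocol names the one fact that decides whether a dosing-day AE preceded the dose, and no SAP rule refers to it. Followed as written, the imputation replaces a known order of events with an assumed one.

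The comparison of safety and tolerability between the combination tablet and the separate tablets is a secondary objective. SAP 17.1.1 tabulates TEAEs by treatment within the fasting and fed groups, and the listings show the treatment at onset. An AE that began before the Day 15 dose could therefore appear under a product the subject had not yet taken. An AE that began before the Day 1 dose could appear as treatment-emergent when no trial drug had been given. Subjects are in house overnight before each dose and are examined before dosing, so AEs in those hours are plausible.

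**Working it through.** The plan gives no figure here, so the check applies the SAP rules by hand, in the SAP's own order, to each kind of AE that starts before the dose on a dosing date. The documents place dosing at around or after 07:00; a dose at 07:30 is assumed for illustration. No worsening after the dose is assumed.

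| Case | Start and end as recorded | Start after SAP 11 | Result under the SAP | Result from the true order |
|---|---|---|---|---|
| 1 | Day 15, start untimed, ongoing at 07:30 or end time unknown (set to 23:59) | 07:30 | Period 2 treatment | Period 1 treatment |
| 2 | Day 15, start untimed, end 06:50 | 07:30 is later than 06:50, so 00:00 | Period 1 treatment | Period 1 treatment |
| 3 | Day 15, start 06:30 recorded | 06:30 | Period 1 treatment | Period 1 treatment |
| 4 | Day 1, start untimed, ongoing at 07:30 or end time unknown | 07:30 | TEAE of the Period 1 treatment | Pre-treatment |
| 5 | Day 1, start untimed, end 06:50 | 00:00 | TEAE under the baseline paragraph, although the imputed start precedes the dose | Pre-treatment |

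Four things follow.

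1. Cases 1 and 4 are misclassified. Cases 2 and 3 are handled correctly.
2. In case 1 the TEAE label is right, because the AE follows the Period 1 dose; only the treatment is wrong. That error comes from the time imputation and the period rule, not from the sentence in the baseline paragraph. The clear error of that sentence is on Day 1.
3. In case 5 the SAP disagrees with itself: the imputed start precedes any dose, so the period rule gives the AE no period, yet the baseline paragraph makes it a TEAE.
4. The period rule requires onset after the dose. A start imputed as exactly 07:30 is neither after the Period 2 dose nor before it, so read strictly it belongs to neither period. The evident intention is that day's period, which is how cases 1 and 4 are traced.

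If the before/during/after record were used first, case 1 would stay with the Period 1 treatment and cases 4 and 5 would be pre-treatment. AEs recorded as during or after would not change.

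Size, with all 16 subjects of a cohort dosed in both periods:

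- One AE wrongly added to, or taken from, a treatment: 1/16 = 6.25 percentage points of incidence.
- One Day 15 AE moved from one treatment to the other: 2 × 6.25 = 12.5 points in the A-B difference.

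Both are ceilings. SAP 17.1.1 counts a subject once per treatment for the same TEAE. The 12.5 points therefore need the moved AE to be the subject's only qualifying TEAE in Period 1, with no other in Period 2.

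**The case against.** The strongest reply is that few AEs will meet these conditions. The onset item asks for date and time, both documents list the time of onset, and the SAP treats an unknown time as the exception, so clock times are probably collected. Staff who notice an event at a timed predose check can write the time down. Abnormal findings become AEs only under the conditions in protocol 7.3.1.1. A subject whose blood pressure before the Day 15 dose is outside the limits is to be withdrawn under protocol 5.5.2, which leaves no Day 15 dose to impute. Safety is descriptive, and imputed values are flagged in the listings, where a careful reader could spot a moved AE. The TEAE default is also deliberate, and described as conservative.

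Most of this stands, and it limits the point to a small class of AEs. Two parts do not dispose of it. First, the default in SAP 17.1 is for AEs whose status cannot be established; a record of onset before the dose normally establishes it, unless the AE worsened. Second, the rule is not conservative on Day 15. The AE already counts as treatment-emergent after the Period 1 dose, so the imputation only takes it from one product and gives it to the other. Flags in the listings do not correct the tables.

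**Conclusion.** The point holds as a minor one. SAP Section 11 contains a rule that misclassifies an untimed AE known to have begun before the dose, contrary to SAP 17.1 and protocol 8.2.4.4. It reaches untimed pre-dose AEs on Day 1, and untimed pre-dose AEs on Day 15 that are ongoing at dosing or have no end time. The ceiling is 6.25 points per treatment per cohort for each AE, and 12.5 points in the A-B difference on Day 15. This assumes all 16 subjects are dosed in both periods, no other qualifying TEAE in the subject, and a start equal to the dosing time being read as belonging to that day's period. The documents do not allow an estimate of how many such AEs there will be.

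A reader might infer three stronger things that the documents do not support.

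- That onset is recorded only as before, during or after, so missing clock times will be common. The wording in protocol 7.3.1.2 is ambiguous, and the listing requirements point the other way.
- That Day 15 pre-dose AEs in general go to the wrong treatment. Those with a recorded start time, or a recorded end before the dose, do not.
- That the main result is at risk. The bioequivalence analysis does not use AE timing from these rules.

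**What to change.** In SAP Sections 11 and 17.1:

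- For an AE on a dosing date without a clock time, let the before/during/after record decide first. Before on Day 1 is pre-treatment and before on Day 15 belongs to the Period 1 treatment, unless the AE worsened after the dose. During or after belongs to that day's treatment.
- Impute the dosing time only if that record is missing too, and make the baseline paragraph agree, including for a Day 1 AE that ended before the dose.
- State that a start imputed as equal to the dosing time belongs to that day's period.

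In protocol 7.3.1.2, or in the eCRF completion instructions, state whether the clock time of onset is collected as well as its relation to dosing.

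The cost is a few lines of SAP text and derivation code before database lock. The eCRF is not among the documents, so first confirm that the relation to dosing is held as its own item.

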#### **Definition of duration:**

Duration will be calculated by the difference of start and stop date + 1 if not otherwise specified. For example, survival time (days) = date of death - the date of first administration + 1.

#### **Conversion factors:**

Unless specified, conversion of days to months /years will be defined as:

1 month = 30.4375 days

1 year = 365.25 days

#### **Common calculations:**

For quantitative measurements, change from baseline will be calculated as:

Test Value at Visit X – Baseline Value

#### Handling of missing data:

Unless otherwise specified, missing data will not be replaced. Handling of missing data for PK parameter calculations are discussed under Section 16.3.3.

In all subject data listings imputed values will be presented. In all listings imputed information will be flagged.

Missing statistics, e.g., when they cannot be calculated, should be presented as "nd". For example, if n=1, the measure of variability (SD) cannot be computed and should be presented as "nd".

For the derivation of new date variables the following rules will apply:

Partial birth dates will be handled this way: day will be imputed as 15 if it is missing, and month imputed as June if missing. If both of day and month are missing, they will be imputed as July 1st. If year is missing then the date will not be imputed.

Any adverse event (AE) with incomplete start and or end dates/times will be handled as described below for the classification as treatment-emergent, assignment to treatment periods and calculation of duration.

• Adverse events with unknown start times but known start dates, will be imputed with a time of 00:00 hours, unless the start date corresponds to any given dosing date, in which

case time of dosing will be used instead. However, if this results in a start time after end time of the AE, then the start time will be imputed to 00:00 hours instead.

- Any adverse event with completely unknown start dates will be imputed with date and time of the first administration of a study drug, unless the end date is known and prior to first administration. In the latter case, the start date will be imputed as the date of screening and a time of 00:00 hours.
- Adverse events with completely unknown end times, will be imputed with an end time of 23:59 hours.
- Adverse events with completely unknown end dates will be imputed with the date of study completion (or in case of withdrawal, date of discontinuation).

Partially known end dates will be treated as follows:

- If only the day is missing, the last day of the month will be imputed or the date of study completion/discontinuation if earlier.
- If day and month are both missing, then the end date of 31 December will be imputed or the date of study completion/discontinuation if earlier.

Assignment to the different treatment periods will be performed after the imputations have been performed. An AE will be assigned to a specific treatment period if it occurs after the IMP administration scheduled for that period and before the IMP administration in the next period (or study completion for the last period).

#### Trial day / treatment day:

Trial day / Treatment day are defined relative to the date of randomization / the date of first administration of trial drug (start of treatment). Trial Day 1 defines the day of randomization, the day before is defined as Trial Day –1 (no Trial Day 0 is defined). Treatment day will be calculated accordingly:

Trial day or treatment day =

- date of event the date of first administration, if date of event < the date of first administration
- or date of event the date of first administration +1, if date of event  $\geq$  the date of first administration

In the situation where the event date is partial or missing, the date will appear partial or missing in the listings, and Trial Day or Treatment Day, and any corresponding durations will be presented as missing. Rules of handling missing dates relevant to efficacy will specified in the subsequent sections.

## 12 Trial Subjects

This section includes specifications for reporting subject disposition and treatment/trial discontinuations. Additionally, procedures for reporting protocol deviations are provided.

## 12.1 Disposition of Subjects and Discontinuations

All subjects who provide informed consent will be accounted for in this study. Subject disposition and withdrawals will be presented for the screening analysis set.

The following summaries will be produced by treatment sequence and overall, for each group:

- Total number of subjects screened (i.e., subjects who gave informed consent)
- Number of randomized subjects
- Number of subjects treated in each period
- Number of subjects that completed each treatment period
- Number of subjects who completed the trial
- Number of subjects who discontinued the study treatment after the first administration, grouped by the main reason
- Number of subjects who discontinued the study, grouped by the main reason
- Number of subjects included in Safety Analysis Set
- Number of subjects included in PK Analysis Set

Corresponding individual listings will be prepared (sorted by group, treatment sequence and subject).

Discontinued subjects will be listed with their reason of withdrawal.

Additionally, a listing of the screening failures will be produced with the reason of non-inclusion in the treatment phase.

Listings with visit dates will also be carried out by group, treatment sequence and subject.

#### 12.2 Protocol Deviations

## 12.2.1 Important Protocol Deviations

Important protocol deviations will be based upon the Clinical Trial Management System (CTMS) data and determined for all subjects by medical review processes. All the important protocol deviations will be included in SDTM datasets, if identified by means of medical review. The Analysis Data Model (ADaM) datasets will be derived from SDTM and include all important protocol deviations.

A data review will be held to discuss and update the definition of important protocol deviations so as to determine the evaluability of the subjects prior to database lock.

The following outputs will be provided by treatment sequence and overall, for each group:

- Summary of important protocol deviations relating to inclusion/exclusion criteria
- Summary of other important protocol deviations

All protocol deviations will be listed. A listing presenting protocol deviations relating to inclusion/exclusion criteria and a listing presenting other deviations will be carried out by group, treatment sequence and subject.

